5.4.5 Termination of Study

There are no stopping rules for the study.

6 STUDY INTERVENTION/INVESTIGATIONAL PRODUCT

6.1 STUDY PRODUCT DESCRIPTIONS

6.1.1 Multimodal Provider Education Intervention

The staff training will be implemented on a team basis within the facilities and will include instruction on how to use a tablet-based IDH prevention checklist during the assessment of every patient. The online training itself will involve a mixture of material for presentation, discussion and online modules to complete independently. The training will be implemented by the University of Michigan Project Coordinator(s). A “Study Champion,” ideally a Clinic Manager or Staff Nurse, will attend a train-the-trainer session with other Study Champions prior to intervention start at their sites. At the training sessions, there will be facilitated discussions regarding checklist implementation so that the facility staff can evaluate how to make checklist implementation fit into their workflows. The checklist is designed to enhance: (1) critical thinking regarding factors which place patients at risk for IDH; and (2) increased focus on IDH prevention in routine hemodialysis care. The checklist has two main parts: (1) four questions to be answered with “yes,” “no,” or “data not available;” and (2) A list of potential treatment considerations for interventions, which are presented as reminders/prompts if any of the answers to the questions are “yes”. In line with the value of team training for patient safety,¹⁵² training will be provided to the care team, and to individuals through a self-study online curriculum. This holds promise for stimulating both collective ownership and for influencing providers’ subjective norms.

The checklist will be made available as an application on an Android tablet computer; the tablet computer, with the checklist application preloaded, will be provided to clinics as part of the study. The checklist will not identify the patient or the staff member, but it will automatically log the facility, date, time, items displayed, and items clicked on a HIPAA-compliant server.

6.1.2 Patient Activation Intervention

We will extend the peer mentoring program offered by the National Kidney Foundation (NKF). Peer Mentors are trained ESRD patients who volunteer to support other patients. Mentors can speak from experience about the challenges of life on hemodialysis; thus patients often view mentors as credible and accessible information sources.^{100, 109-111} Mentors can role model health behavior change as they share their experiences.¹¹⁰

Peer mentoring model. NKF's telephone-based peer mentoring model for ESRD patients is flexible and compatible with rigorous hemodialysis schedules. The mentor's current role is to provide social support to other patients; this will be expanded in the intervention to include teaching and motivation with appropriate training and multimedia support. Peer mentoring sessions will incorporate behavior change techniques drawn from SCT,¹⁵⁰ including providing information about cardiovascular complications related to hemodialysis, teaching skills, encouragement, and role modeling (Figure 1). To enhance motivation, mentors will use MI techniques, including exploration of feelings and personalized goal setting. *Peer Mentor Selection.* Peer Mentors must: (1) have dialysis experience, and (2) not have an active substance use disorder, disorders with psychotic features, or suicidal ideation.¹⁵¹

Peer mentor-mentee matching. Mentees will undergo an intake procedure with NKF staff to understand the patient's characteristics, interests, illness experiences/challenges; these data will be used to match compatible mentors with them.

Peer mentor training. The training manual has been adapted from NKF's existing curriculum in consultation with peer mentors and the Advisory Committee. There will be multiple training cycles over the course of the project. Training will be seven hours long, divided into 10 self-paced training modules, with one live, virtual training session for role plays and mentor skill assessment. Training will include information on (1) the role of the peer mentor, (2) cardiovascular stability, (3) listening and communication skills, including MI techniques, (4) sharing experiences and strategies; (5) confidentiality and boundaries, and (5) program protocol/logistics such as using multimedia tools, intervention fidelity and record-keeping (see Figure 1). Peer mentors will be trained to refer patients with obvious symptoms of depression or other mental health issues to NKF staff. Trainers for the peer mentor program training will consist of NKF staff and peer mentors; they will receive training on motivational interviewing. To ensure mentors have gained needed skills, each mentor will be assessed during role plays. The fidelity of training sessions will be tracked with the use of checklists.

Peer mentors will receive human subjects training using Harvard Catalyst's Community Partner Human Subjects Training, as suggested by UM IRBMED. We have been granted permission to modify the training in the following ways:

- 1) All materials will be delivered through Canvas, the online learning tool used for coursework at the University of Michigan
- 2) Prior to the first live seminar training, all peer mentors will be enrolled in a "class" using their personal email addresses
- 3) The educational slide deck will be divided into thematic sections and made into short videos with voice over
- 4) Each video will be accompanied by the quiz. This quiz will contain the part of Harvard Catalyst's suggested assessment that relates its respective training section. Some questions may be modified to make them more relevant to the Dialysafe project. The quiz may be re-taken in the case of wrong answers.
- 5) Study staff will monitor activity on the Canvas page to ensure that each mentor watches each video and completes every quiz. Those who complete every section of the video/quiz course will receive a certificate of completion.
- 6) The first live seminar will include a discussion section regarding the training, including examples tailored to study-specific scenarios, edited from the last portion of the catalyst training.

Harvard Catalyst will receive attribution credit on all materials.

6.3 MODIFICATION OF STUDY INTERVENTION/INVESTIGATIONAL PRODUCT FOR A SUBJECT

N/A

6.4 ACCOUNTABILITY PROCEDURES FOR THE STUDY INTERVENTION/INVESTIGATIONAL PRODUCT(S)

Tablet computers for both multimodal provider intervention and the patient activation intervention will be configured by the study team. Tablet computers for the provider intervention will be shipped to each dialysis center; tablet computers for the patient activation will be shipped directly to the patient's home or skilled nursing facility by the study team. Facilities will be able to keep the tablet computers and charging stations at the end of the study period.

In the event that a patient is interested in joining the peer mentoring program but does not have regular access to a phone to contact UMSI study staff and/or NKF, a pre-paid cell phone will be provided for the patient to use. The phone will be shipped to the patient's home address with a limited number of minutes pre-loaded for their use. At the end of the study, the phone may be discarded, or the patient may choose to purchase more minutes and retain the phone as a personal device. The pre-paid phone is not considered an incentive because it will not be preloaded with enough minutes to be used for personal use. The estimated value of the phone without minutes is \$25. Neither study nor clinic staff will have the ability to track the phone's use after it has been activated by the patient.

In the event that a patient has joined the peer mentoring program but is unable to connect their tablet to a secure and reliable internet connection, we will send a mobile hotspot. The mobile hotspot will be returned at the completion of the peer mentoring program along with the tablet.

6.5 ASSESSMENT OF SUBJECT COMPLIANCE WITH STUDY INTERVENTION/INVESTIGATIONAL PRODUCT

Intervention fidelity tracking methods will include data automatically collected as part of digital interventions, as well as checklists manually completed by UM and National Kidney Foundation Study Coordinators and peer mentors. These data collection methods include:

- *Checklist completion*, which includes date/time-stamped records of each checklist completion session, logins to identify the facility at which it was completed, and records of buttons clicked and screens displayed.
- *Patient Intervention completion*, which includes records of completed peer mentoring sessions by patient login, with date, time, session length, and the number of people present at the session. Additionally, it will record patient views of specific content on the tablet-based peer mentoring education, as well as length of time spent viewing each part of the content.
- *Peer Mentoring Fidelity*. Peer mentors will use a checklist to record their coverage of all required content as part of each mentoring session. The checklist will include items such as whether the patient understands the benefits of getting enough dialysis, and whether the peer mentor has encouraged the patient towards reaching a behavioral goal.
- *Staff Training Fidelity*. UM Study Coordinators will use a checklist to record their coverage of all required content as part of each online, staff-delivered training session, and record attendance by role at the sessions. FMCNA's learning management system (LMS) will also produce reports for each facility regarding the number of staff in each role who have completed two LMS training sessions. Similarly, FMCNA staff will provide this information to UM Study Coordinators for the online sessions via UM Study Coordinators' FMCNA email accounts.
- *Patient Technology Training Fidelity*. Patient who join the peer mentoring program will be offered a "tech training call" to ensure that they are comfortable with the study-provided tablet. UM study staff will use a checklist (see "Dialysafe_pt_tablet_training_plan") to record items discussed during the training call, including: how to navigate the tablet and website, any major issues or questions, the start and stop time of the call, the date of the call, and the name of the UMSI staff member providing training. No identifying patient information will be recorded.
- *Patient Technology Training Recruitment Records*. UM study staff will track the number of patients receiving peer mentoring who accept or decline a tech training call. Whether training was accepted or refused, the reason for refusal (as applicable), and whether

training was completed and/or rescheduled will be recorded. (See “tech calls” log.) No identifying patient information will be recorded.

- *Tracking Technical Support.* UM study staff will log questions received from calls to the study 1-800 number, and/or emails from clinic staff. The question, whether it was solved, and the type of participant making the inquiry (clinic staff/patient/peer mentor) will be recorded along with the time, date and name of the UMSI study staff addressing the question. (See “tech calls” log.) No identifying patient information will be recorded.

We will use the captured fidelity data to create and track the following metrics:

- Staff Checklist
 - Checklist completion rate by facility over specific time points (number of completed checklists / number of patient sessions (for patients included in the study) calculated over a given time period (e.g., a month)
 - Proportion of checklist sessions in which patients are identified as being at risk of IDH
 - Prevalence of reasons why patients were identified as being at risk of IDH
- Staff Training
 - Proportion of staff by role who completed each training session, tracked by facility
 - Average proportion of training elements completed
 - Proportion of training sessions in which all training elements completed
- Patient Intervention
 - Average number of mentoring sessions completed per patient
 - Patient retention rates across all five peer mentoring sessions
 - Average peer mentoring session length
 - Education module completion rates by topic and section
 - Quiz completion rates
 - Average time spent on each educational module section
 - Average proportion of peer mentoring session components completed by session
 - Proportion of peer mentoring sessions in which all session components completed
 - Mentor-specific peer mentoring completion rates – for use by NKF in training and supporting mentors

6.6 CONCOMITANT MEDICATIONS/TREATMENTS

N/A

7 STUDY SCHEDULE

The active intervention will begin in sets of four clinics at a time, each randomized to one of four treatments. See Schedule of Events in Appendix A for staggered roll out dates. The study coordinator will contact each clinic manager by phone -7 to -4 months from data collection start. The Study Coordinator helpline will be available during the preparation and enrollment periods, one month prior to data collection, in order to assist with patient or clinic questions. The study coordinator will schedule digital meetings for each provider education clinic in intervention weeks 1-3 to conduct the first online training and in weeks 4-6 to conduct the second online

training. Study coordinator(s) will be available by phone for questions or concerns throughout the study. See the Schedule of Events for an overview of the study schedule.

The patient activation intervention should take 5-6 weeks on average to complete. We anticipate staggered participation of patients in the patient activation intervention due to limits on the number of tablet computers and the number of peer mentors.

7.1 SCREENING

To ensure national representation, a list of 60 candidate regions covering the Midwest, Northeast, Southeast and Southwest were generated. From these areas, all eligible facilities are returned from the FMCNA corporate data warehouse with a query applying the following eligibility criteria: (1) outpatient HD facilities, (2) at least 70 adult patients (≥ 21 years of age), (3) not involved in other Frenova research, (4) facilities with two to five stars in CMS's Dialysis Facility Compare; (5) not in immediate jeopardy in previous two years, (6) not a facility in which the entire facility has been designated for isolation of patients with suspected or confirmed COVID-19, and (7) not a Kaiser facility. A list of facilities within candidate regions meeting criteria 1-7 will be generated. Facility randomization procedures will then be performed on this list.

Patients within clinics will be screened for vulnerable status. Patients will be screened in two ways per Table 3 below: 1) By the FMCNA Custom Reporting and Data Analytics group team for electronically available criteria, and 2) by the local clinic team (Clinical Manager, Medical Director, Social Worker) for criteria not electronically available.

Table 3 – Screening for Patient Vulnerable Status		
Criteria	Determined Electronically	Determined by Local Clinic Team
Exclusion Criteria		
Age < 21 years old	✓	
Transient Patients	✓	
Acute Renal Failure	✓	
Prisoner		✓
Cognitive Barrier (poor cognition or cognitive impairment)		
Patients who were excluded from the most recent KDQOL on basis of poor cognition (determined by social worker)	✓	
Per the judgement of the Clinical Manager, Medical Director, and Social Worker, with consultation with the Medical Attending as needed, regarding: Cognitive impairment. As needed, the Social Worker may utilize existing policy for Cognitive Functioning Assessment that utilizes the Montreal Cognitive Assessment-Basic tool.		✓
Patient is unable to comprehend the patient information sheet due to lack of facility in English or Spanish (patients whose primary spoken language is not English or Spanish)		✓

Those deemed vulnerable per above will not be included in the study. All other patients will be given the opportunity to opt out of the study if desired.

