We aim to include all non-vulnerable in-center patients at participating dialysis facilities. The trial is designed so as not to exclude anyone, including women and minorities to the extent they are represented at the dialysis facilities from the ages of 21 and older. We will only exclude vulnerable patients: those under 21 years of age; prisoners; those with a cognitive barrier (poor cognition or cognitive impairment); those deemed vulnerable by the Clinical Manager, Medical Director, and/or Social Worker (see Table 3: Screening for Patient Vulnerable Status), and those who are unable to comprehend the patient information sheet due to lack of facility in

English or Spanish. This will counter selection bias by ensuring that participants are representative of the full spectrum at a given facility. Selection bias is a risk in a peer mentoring intervention for a seriously ill population because patients who are comparatively less sick, and more motivated to manage their health actively, may be more likely to participate. The difficulty with such selection bias is that the study participants could be part of a subgroup of people who may have improved on their own, without the intervention. Therefore, improvements in outcomes may be erroneously attributed to the intervention. Our planned approach minimizes the likelihood of such mistaken conclusions. With regard to peer mentoring only, we will randomly select patients who are not vulnerable or have not opted out of the study in succession, until approximately a maximum of 30 patients in a facility finish peer mentoring (with partial data on at least 6 patients who start but do not finish). That is, every time a patient declines to participate, we will choose another patient randomly until the enrollment target is reached. Due to limited availability of peer mentors fluent in languages other than English, only English-speaking patients will be offered peer mentoring.

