5.3 STRATEGIES FOR RECRUITMENT AND RETENTION

In order to recruit facilities, the FMCNA Project Manager has approached/will approach regional management (regional vice presidents, RVPs) at FMCNA to educate them regarding the study process. After screening of facilities by FMCNA based on inclusion criteria and random selection by UM from the pool of eligible facilities, these RVPs were/will be approached and their approval sought, on a voluntary basis. At that time, RVPs have assessed/will assess whether facilities were/are adequately staffed to participate in the study and have considered/will consider the level of staff effort required in the context of other ongoing FMCNA and CMS initiatives. RVPs have management authority over their regional clinics and were/will be able to facilitate clinic recruitment. The RVP or the FMCNA Project Manager has approached/will approach the medical director of the randomly-selected facilities, and each facility's management body (called Governing Body) will approve study participation.

If a facility declines to participate, we will approach the next randomly-selected facility until the recruitment goal for the region is reached. Once recruited, facilities will also be randomized into study arms. If a facility drops out of the trial, the UM team will select another eligible facility to participate in the trial according to the clinic inclusion criteria and recruitment process used for the initial clinics.

We plan to include all non-vulnerable patients at participating dialysis facilities who do not opt out of the study. The study population of patients enrolled in this trial will be representative of the general adult hemodialysis population in the United States with respect to age and health status (e.g., typically with multiple comorbid conditions, including diabetes, hypertension, and cardiovascular disease). Our target subject sample is approximately 1,200-1,440 patients across the 20 facilities will be enrolled in the study (see attached Performance Site Listing). It is anticipated that there will be more than adequate representation by minorities as these are typically over represented in the dialysis population and also because of the geographic diversity of participating sites (e.g., Michigan, Ohio, California, Alabama, Massachusetts and Connecticut). Health care providers will not be study subjects.

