5.4.2 Blinding Procedures

Study participants and facilities will not be blinded to treatment status. However, during the initial analyses, study analysts will be blinded to treatment status in that they will not know which facilities are in which intervention group. Each intervention group will be given a non-identifying code, and each facility assigned to one of those codes (e.g., group A, group B, group C) while a list of facilities by treatment status is kept separate during the analyses. Analyses will then be conducted using intervention group codes that do not reveal which intervention in which a facility is participating. Supplementary as-treated analyses cannot practically be completed in a blinded fashion due to heterogeneity of measures (e.g., number of peer mentoring sessions completed by a patient).

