10 CLINICAL MONITORING

10.1 SITE MONITORING PLAN

I. Study Governance

FMCNA and NKF will participate in the study in accordance with executed subcontracts. Prior to participation in the study, each facility's Governing Body will review study materials and approve participation.

II. Study Champion

The Medical Director and Clinical Manager at each site with an intervention (n=15; the 5 clinics doing data collection only will not have a Study Champion) will then identify a “Study Champion,” who will ideally be a Clinic Manager or Staff Nurse. Each Study Champion will attend a train-the-trainer session with other Study Champions prior to intervention start at their sites. The Study Champion will speak with a University of Michigan Project Manager at least monthly during the trial in study facilities. The Study Champion’s role will involve:

- Participating in quarterly Operations Committee meetings (to take place during the baseline and intervention periods)
- Serving as a liaison to provide staff feedback to the University of Michigan Project Coordinator(s).
 - Examples: Post a study comments notebook in the break room, accept verbal comments from staff, and convey comments during Operations Committee calls.
- Co-leading with Clinical Manager, discussion about checklist implementation at two staff meetings
- Updating the Research Binder with current patient lists and any other updated documents throughout the study
- Conveying positive messaging about the study

III. Operations Committee

An Operations Committees will be formed in each study facility with an intervention (no Operations Committee will be formed for clinics randomized to data collection only); this Committee will include staff members in authority positions such as the local Clinical Manager and Directors of Operations. The Clinical Manager is accountable for the operation of the facility, has authority over the staff in his or her assigned clinic, and has physical presence in the clinic on a regular basis. The Director of Operations is accountable for a group of clinics in the geographic area, and has authority over the Clinical Manager. The Operations Committee will meet three times over the course of the study, and include the Study Champion as per above, and others selected to represent different organizational levels and perspectives. Patient representatives (n=1-2) will also participate in the Operations Committee and will be selected based on the following criteria:

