- 1) Not excluded from the study on the basis of vulnerable status or opting out
- 2) Access to email for receipt of meeting materials
- 3) Sufficient English ability to participate in meetings (English as primary language)
- 4) Sufficient hearing ability to participate in meetings by phone (per patient’s judgement)
- 5) Nomination by Clinic Manager, or self-nomination.

The Operations Committee will oversee intervention implementation in each of the study facilities. At the meetings, the UM Study Coordinator will provide feedback to the facility regarding intervention fidelity (e.g., checklist completion rates, staff training completion rates, patient retention rates across all five peer mentoring sessions). Feedback will be sought from facility staff regarding the intervention, and its impact upon facility operations. The Committee will also engage in collective problem-solving as needed as led by the UM study coordinator, who will schedule, plan, organize and lead Operations Committee meetings.

IV. Role of Medical Director at Study Facilities

In addition, the Medical Director at each site will communicate initial study information to medical colleagues (attending nephrologists and other providers) in the facility, and then communicate as needed to these colleagues throughout the study. In order to increase the appeal of participation, UM has also incorporated a total of \$500 divided into two payments (\$250 each payment) for each of the Medical Directors of study facilities in the project budget for carrying out their responsibilities related to the study as described below. UM will be responsible for managing the payment process. Each payment will be triggered by completion of the Practice Patterns Survey associated with that payment (see attached Practice Patterns Survey - Medical Directors and Practice Patterns Survey - Nurse Managers).

Payment #1 of \$250 shall be compensation for the following activities:

- Participate in the process of Governing Body approval for the study.
- Communication of initial study information to medical colleagues (attending nephrologists and other providers) in the clinic.
- Work with Clinical Manager to identify a Study Champion, if applicable.
- Work with Clinical Manager to identify patients deemed vulnerable that should be excluded from the study, per the study's exclusion criteria.

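### Cognitive-impairment exclusions rest on clinic leaders' judgement in facilities already randomised and unblinded, and nothing fixes the list before the arm is disclosed

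*Combined protocol and SAP*

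**What the plan says.** Section 7.1 divides patient screening in two. Age, transient status, acute renal failure and a previous KDQOL exclusion for poor cognition come from electronic records. The remaining criteria are assessed "by the local clinic team (Clinical Manager, Medical Director, Social Worker) for criteria not electronically available". For cognitive impairment, Table 3 relies on the judgement of these staff. Formal testing is optional ("As needed, the Social Worker may utilize existing policy for Cognitive Functioning Assessment") and no cut-off is given. Sections 2.2.2 and 5.2 can be read as letting any one of the three decide, whereas Table 3 names them jointly. The consequence is exclusion: "Those deemed vulnerable per above will not be included in the study".

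On timing, section 5.3 says "Once recruited, facilities will also be randomized into study arms", and section 5.4.2 says "Study participants and facilities will not be blinded to treatment status". Under section 10.1, only the 15 intervention sites name a Study Champion or form an Operations Committee. The first Medical Director payment covers naming the Champion where applicable, and also this task: "Work with Clinical Manager to identify patients deemed vulnerable that should be excluded from the study". Section 7.2 continues enrolment of new patients until 8 weeks before the intervention period ends.

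Section 2.2.2 says of its near-universal inclusion: "This will counter selection bias by ensuring that participants are representative of the full spectrum at a given facility".

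**The concern.** A cluster trial keeps the benefit of randomisation only if the patients who enter are selected in the same way in every arm. Here a discretionary criterion is applied after allocation, by people who are not blinded and who lead the clinic. A clinic that expects its patients to use tablets and video calls (section 6.2.2) might draw the line on cognitive impairment differently from one that does not.

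The plan treats this kind of bias as serious. Section 14.3 asks for participation as close to complete as possible, and it rejects individual consent partly because consent could unbalance the arms. If judged-impaired patients have a different rate of IDH, hospitalisation or death, unequal exclusion would produce a difference between arms without any treatment effect. Excluded patients contribute no outcome data, so the difference could not be repaired in the analysis.

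**Working it through.** **1. Order of events**

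- Allocation: at facility recruitment (5.3). Clinics start in sets of four that are already randomised (section 7).
- Signs of the arm: a Study Champion and an Operations Committee exist only at intervention sites, and committee meetings take place during the baseline and intervention periods (10.1).
- Initial census: Table 2 starts each group's data period three months before initial enrolment opens (Group 1, for example: October 2022 and January 2023). Committee meetings in the baseline period could therefore precede initial screening. This makes knowledge of the arm likely, but no sentence dates the vulnerability screen against disclosure.
- Later entrants: screened while the intervention is running, so the arm is known. Section 5.4.1 expects 15-20% of patients to be replaced over the 11 months.

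**2. The plan's own figure (section 11.2, Table 5)**

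Inputs: 10 facilities per group, 60 patients each, ICC 0.10, significance level 0.05 (taken as two-sided), SD 0.08 or 0.10.

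- Design effect = 1 + (60 − 1) × 0.10 = 6.9. Effective n per group = 600 / 6.9 = 86.96.
- SE = SD × √(2 / 86.96) = 0.01213 (SD 0.08) or 0.01517 (SD 0.10).
- Power = Φ(D/SE − 1.96) gives 80.0%, 61.1%, 90.9% and 80.9%. Table 5 has 80%, 61%, 91% and 81%.

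Table 5 reproduces and is not in dispute. Its SE serves as the yardstick below.

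**3. Illustration of size (exclusion and IDH gaps assumed)**

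If one arm removes an extra share x of patients, and their IDH is g points above that of the patients who remain, the arms differ spuriously by x × g.

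- 0.05 × 10 = 0.5 point; 0.10 × 10 = 1.0 point.
- Against the planned difference: 0.5 / 4.3 = 12%; 1.0 / 3.4 = 29%.
- Two-sided type I error = 1 − Φ(1.96 − b/SE) + Φ(−1.96 − b/SE), where b is the bias. It is about 6-7% for b = 0.005 and 10-13% for b = 0.010, depending on the SD.

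A wider grid assumes that 20% of patients could be judged impaired, that IDH is 20% in the others, and that impaired patients have d = 5 to 15 points more. With a share e excluded, mean IDH among those enrolled is [0.20 × 0.80 + (0.20 + d)(0.20 − e)] / (1 − e). For exclusion of 5% v 10%, 5% v 15% and 10% v 18%, the spurious difference runs from 0.23 to 1.49 points, which is 7% to 44% of 3.4 points. Type I error runs from about 5.3% to 23%. With equal rates and criteria the bias is zero.

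For scale, section 14.3 expects 1,400 patients to fall to 1,200: 200 / 1,400 = 14.3% for all vulnerability reasons and opt-outs together. A 10-point gap between arms would be 10 / 14.3 = 70% of that total, so the upper end is extreme.

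**4. Which contrast is exposed (section 4.1, Table 1)**

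The mentoring effect compares A+C with B+D, so all ten mentoring clinics are on one side. The provider effect compares A+B with C+D, with five mentoring clinics on each side. Exclusion driven by mentoring enters the first contrast fully and largely cancels in the second.

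**5. Late entrants and the 60-session rule (section 11.4)**

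At three sessions a week, 60 sessions take 20 weeks. Within the 24-week intervention, a patient entering after about week 4 cannot qualify. If the 12-week follow-up also counts, entry up to about week 16 (36 − 20) can qualify. Section 11.4 says only that data come from the study period. The GLIMMIX sensitivity model has no minimum and includes all late entrants.

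**The case against.** The strongest reply is that disclosure before the initial screen is not documented. The tasks under the Medical Director's payment are a list, not a chronology. The opt-out procedure and the Schedule of Events, which might settle the order, are attachments not reproduced here. Section 2.1.1 has staff learn their study group in training part 1, and the patient information sheet described in section 7.2 is neutral as to arm. This stands: a reader might infer that site leaders know their arm whenever they screen, but the text supports that only for later entrants.

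The motive is also inferred. Mentoring is offered by university staff by telephone to a random subset, patients may decline and are then replaced, and tablet training is available. A clinic need not exclude anyone to keep that patient out of mentoring. In provider clinics, checklist completion is divided by the sessions of included patients (6.5) and carries incentives (4.1), but nothing suggests that this would affect screening.

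Safeguards exist. Poor cognition recorded at the last KDQOL is removed electronically, which leaves a smaller group to local judgement. The language criterion is tied to primary spoken language. Section 11.4 compares the enrolled groups for selection bias and adjusts for age, education, literacy and comorbidity. Unequal removal of frail patients could show up there as imbalance. The protection is partial: cognition is not a named covariate, and the section 15.6 audit compares opt-outs with study orders, not vulnerability decisions.

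Local judgement of capacity is a legitimate protection for patients. The point concerns when the judgement is made and recorded, not who makes it.

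**Conclusion.** The concern holds as a gap in procedure. A judgement-based exclusion is applied in randomised, unblinded facilities, and no section fixes the list before disclosure. Knowledge of the arm is certain for patients entering during the intervention and likely, by inference, for the initial census. Enrolled populations can therefore differ by arm, chiefly in the mentoring contrast. The 60-session rule limits what late entrants can do to the primary model but not to the all-patient model.

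A reader might go further and conclude that the interventions will look better than they are, or take 0.5 to 1.0 point as an estimate. The documents support neither. They give no exclusion rate by arm and no IDH rate in impaired patients, so size and direction are unknown and the figures hold only under the stated assumptions. The gap is worth closing because doing so costs little.

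**What to change.** 1. In section 7.1, for implementation groups not yet told their arm, require each clinic to complete its Table 3 judgements for the current census and lock the list before disclosure. This reorders start-up steps. The downside is that the Study Champion is named slightly later. Table 2 estimates that the last initial enrolment ends in February 2024, so the sponsor must establish whether any group can still benefit.
2. In section 11.4, for all groups, add a sensitivity analysis of the primary outcome restricted to patients on the initial screening list, for both the linear mixed model and the all-patient GLIMMIX model. State that it addresses late entrants only and does not correct an initial list drawn up with the arm known. The cost is one extra run of each model.
3. Report exclusions by Table 3 reason, and opt-outs, as counts per facility and arm, so that differential exclusion can be seen. This needs a tally kept at screening and no further patient data.
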